distinguish VTE patients who have low recurrence risk (annual rate, 3.0%) and can discontinue anticoagulation from those who have, in contrast, a high risk of recurrence and deserve extended anticoagulation. It was also found that after 12 months of anticoagulation the rate of recurrent events was not different in subjects with or without residual vein thrombosis. In the DULCIS study, however, the rate of major bleeding complications in those who resumed VKA anticoagulation was substantially high (3.7%; 2.3% annually). In addition, the number of patients older than 70 and that of patients with isolated PE was not high enough to yield robust conclusions.

The use of D-dimer assessment after anticoagulation is stopped has also been suggested by the latest ACCP guidelines ³ as a tool to guide deciding on extended anticoagulation or not.

AIM OF THE STUDY

The main aim of this prospective cohort study is to assess the efficacy and safety of a management procedure to decide on giving or not an extended anticoagulation (administering apixaban 2.5 mg BID) to outpatients with a single episode of proximal DVT of the lower limbs and/or PE who had received 12-18 months anticoagulation (whatever the anticoagulant drug used). The study seeks to assess whether a management procedure involving D-dimer testing assessment can identify a subset of subjects at low risk of recurrence in whom an extended anticoagulation can be safely avoided.

STUDY DESIGN

Phase IV, multicenter, national, prospective cohort study

STUDY POPULATION

The study includes outpatients with a single episode of venous thromboembolism (VTE), at a first episode of proximal deep vein thrombosis (DVT) and/or pulmonary embolism (PE), whose pathogenesis is either unknown (unprovoked VTE) or associated with weak risk factors for thrombosis, who had received 12-18 months anticoagulation (whatever the anticoagulant drug used).

SCREENING OF PATIENTS AND INCLUSION/EXCLUSION CRITERIA

Screening and inclusion of patients

All consecutive patients who have experienced a single episode of proximal DVT of the lower limb and/or PE that was unprovoked or associated with a risk factor that was removed (see Table 1), and have completed 12-18 months of anticoagulation (whatever the drug used) will be screened by the participant centers when they are still being treated with anticoagulants and the screening form completed.

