2) D-DIMER ASSESSMENT

Patients included in both Subgroups of the study are invited to undergo D-dimer measurements. They are informed that:

- a) the cut-off value used in the study can be different than the limit values shown in the laboratory reports of the tests;
- b) in case D-dimer assay would give a positive result (above the study cut-off value established for the used assay) they would be advised to continue anticoagulation or, if anticoagulation has already been stopped, to resume anticoagulant treatment by assuming in both cases the novel direct oral anticoagulant drug apixaban (Eliquis) 2.5 mg BID, provided by the study, that is associated with a low risk of bleeding, according to the currently available scientific literature. The patients will then receive a serial determination of D-dimer assay (a maximum of four determinations in case of negative results) by using the routinely locally adopted method assay (provided it is one of those listed in Appendix 1).

The D-dimer measurement should be performed at the moment of patient screening, when patients still assume their anticoagulant treatment (T0), and at 15±2 days (T1), 30±4 days (T2), and 60±5 (T3) days after their anticoagulant treatment has been stopped.

Patients with a positive D-dimer assay who may refuse to continue anticoagulation will be followed for the next 18 months.

Patients with positive D-dimer results at T0 (see Appendix 1 for D-dimer cut-off levels according sex) are offered to continue anticoagulant treatment by shifting to receive apixaban (Eliquis) 2.5 mg BID. If they accept to be treated with apixaban they are included in the study and followed-up for 18 months; if they decide to continue their current anticoagulant treatment (different than apixaban 2.5 mg BID) they are excluded from further participation in the study. Patients with negative D-dimer result at T0 are invited to stop assuming their anticoagulant therapy and continue on serial D-dimer measurements. At the first positive D-dimer result in serial testing, they are invited to resume anticoagulation by assuming apixaban (Eliquis) 2.5 mg BID.

Patients with persistently negative results of the four serial D-dimer measurements, are invited to stay definitively without anticoagulation and discouraged from resuming any antithrombotic drug for secondary VTE prevention.

3) RESUMING ANTICOAGULATION: APIXABAN

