 - ✓ current or recent gastrointestinal ulceration, presence of malignant neoplasms at high risk of bleeding, recent brain or spinal injury, recent brain, spinal or ophthalmic surgery, recent intracranial hemorrhage, known or suspected esophageal varices, arteriovenous malformations, vascular aneurysms or major intra-spinal or intracerebral vascular abnormalities;
 - ✓ concomitant treatment with any other anticoagulant agent e.g., unfractionated heparin (UFH), low molecular weight heparins, heparin derivatives (fondaparinux, etc.), oral anticoagulants (warfarin, rivaroxaban, dabigatran, etc.) except under specific circumstances of switching anticoagulant therapy or when UFH is given at doses necessary to maintain an open central venous or arterial catheter.

The patients with one of the absolute contraindications to Eliquis are invited to resume anticoagulation using a different anticoagulant drug.

FOLLOW-UP AND STUDY END-POINTS

All patients included in the study, a) those with persistently negative D-dimer who stopped anticoagulation, b) those with positive D-dimer who continued or resumed anticoagulant treatment by assuming apixaban 2.5 mg BID, and c) those with positive D-dimer who may refuse to assume apixaban as well as any other anticoagulant or antithrombotic agent for secondary VTE prevention, will be followed up for at least 18 months after recruitment in the study. They will be examined or interviewed telephonically every 3-6 months in order to assess their health conditions and to check the occurrence of events. All primary events occurring during the follow-up, including objectively proven recurrent VTE, major or clinically relevant non-major bleedings and deaths from any cause will be objectively documented according to widely accepted guidelines and recorded. All the events will be adjudicated by a central adjudication committee. All the patients are invited to immediately refer to the enrolling center at the appearance of signs or symptoms compatible with venous thromboembolism or other complications (such as bleeding episodes).

Primary efficacy end-point: the composite of confirmed recurrent VTE and VTE-related death occurring during follow-up in all included patients

Primary safety end-point: major bleeding ¹¹ complications occurring during the follow-up period in all included patients

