Targeted Physical Examination	X				X	
Vital Signs	X					
Assessment of Signs and Symptoms	X				X	
Compression Ultrasound Doppler (CUS) evaluation	X					
Echocardiography evaluation	X					
Pregnancy test	X					
D-Dimer Test	X	X				
Follow up every 3-6 Months until 18 months		X	X	X		
Clinical Drug Supplies						
Dispense Study Treatment			X			From the first

Procedure	Screening Visit (T0)	D-Dimer test T1, T2, T3			Last Visit	Notes
		Patient with negative D-Dimer	Patient with positive D-Dimer	Patient with positive D-Dimer who refuse Apixaban		
						positive D-Dimer test Apixaban will be dispensed every 6 months
Efficacy End Points						
Primary		X	X	X	X	
Secondary		X	X	X	X	
Safety End Points						
Primary		X	X	X	X	
Secondary		X	X	X	X	

STATISTICAL CONSIDERATIONS

The aim of this management study is to demonstrate that in patients with a first unprovoked VTE a combination of a prediction rule based on D-dimer and low-dose DOAC in those at higher recurrence risk result in a recurrence risk comparable to the population of patients with provoked VTE.

Assumptions

based on the results of the DULCIS study¹⁰, approximately 45% of all eligible patients are expected to discontinue anticoagulation, with an annual rate of recurrent VTE events around 3% (95% 2.0 to 4.4%).

In the remaining 55% of patients who will be encouraged to use apixaban, based on the results of the Amplify Extension study the expected rate of recurrent VTE is around 1.7% after the first year of treatment.

Based on the metanalysis¹² the annual recurrence risk in patients with provoked VTE is 3.3%

Based on these assumptions, we expect the recurrence rate at 12 months to be:

$$0.45*0.03+0.55*0.017=2.2\%$$

Sample size: With an expected annual recurrence rate of 2.2% in the APIDULCIS population, we calculated the sample size to demonstrate, with an 80% power, that the 95% CI is below 3.5% according to Shen¹². The required sample size is 1148 patients to be recruited for the purpose of the APIDULCIS study.

Kaplan–Meier survival curves will be plotted to estimate the cumulative incidence of symptomatic recurrent VTE; hazard ratios (HR) and their 95% confidence intervals (CI) will be calculated for subgroup analyses.

Safety end-points and interim analysis

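### Membership of the untreated group is settled only at about day 60 after stopping, while follow-up starts at recruitment, so the untreated rate and the interim hazard ratio can be biased if the groups are used as written

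*Protocol*

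**What the plan says.** The section on follow-up and end-points sorts all included patients into three groups: (a) "those with persistently negative D-dimer who stopped anticoagulation"; (b) D-dimer positive and taking apixaban; (c) D-dimer positive and refusing apixaban and any other antithrombotic. They "will be followed up for at least 18 months after recruitment in the study".

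The D-dimer assessment section fixes what membership of (a) requires: "Patients with persistently negative results of the four serial D-dimer measurements, are invited to stay definitively without anticoagulation". After T0, which is taken on treatment, the tests fall at "15±2 days (T1), 30±4 days (T2), and 60±5 (T3) days after their anticoagulant treatment has been stopped". Stopping comes earlier: "Patients with negative D-dimer result at T0 are invited to stop assuming their anticoagulant therapy and continue on serial D-dimer measurements".

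The primary efficacy end-point is "the composite of confirmed recurrent VTE and VTE-related death occurring during follow-up in all included patients". The aim section adds a question that rests on the untreated patients alone, namely whether the procedure "can identify a subset of subjects at low risk of recurrence in whom an extended anticoagulation can be safely avoided". The interim rule, under safety end-points and interim analysis, would stop the study if the hazard ratio for the untreated observation arm exceeds 3 with p<0.0001. It does not say which of groups (a) to (c) make up that arm.

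**The concern.** Group (a) is defined by a result that does not exist until about two months after the patient has come off anticoagulation. A patient who is negative at T0 and T1 and recurs on day 20 has not completed four negative tests, has no positive test, and has neither taken nor refused apixaban. The list is meant to cover everyone but gives this patient no place. The study assessments section repeats the list and adds only patients with premature discontinuation, a term the protocol uses for stopping study treatment, which this patient never took.

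Anyone who does reach group (a) has by definition got through the window without an event. If that window is also counted as follow-up time, it is immortal time. The same holds on the other side: a patient who turns positive at T1, T2 or T3 has already spent 15 to 60 days off drug without a recurrence, and classification by eventual group credits that time to apixaban.

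Two uses are exposed: the untreated rate on which the low-risk-subset aim depends, and the interim hazard ratio.

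**Working it through.** **Inputs, all from the protocol.** About 1150 patients, 18 months of follow-up and an overall rate of 2.2% per year (interim section). For the untreated, "approximately 45% of all eligible patients are expected to discontinue anticoagulation", at 3% per year with interval 2.0 to 4.4%; for apixaban, 1.7% at one year (statistical considerations). Window from stopping to T3: 60 days, range 55 to 65 (D-dimer section).

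**The plan's own figure.** 1150 × 0.022 × 1.5 = 37.95, the 38 recurrences stated.

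**Expected untreated events over 18 months.**
- Patients: 0.45 × 1150 = 517.5
- Person-years: 517.5 × 1.5 = 776.25
- Events: 776.25 × 0.03 = 23.3

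**Of these, before T3, at a constant hazard.**
- At 3%: 517.5 × 0.03 × 60/365.25 = 2.55
- At 2.0%: 1.70; at 4.4%: 3.74

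**Rate if early events are left out but time runs from stopping.**
- (23.29 − 2.55)/776.25 = 0.0267, so 2.67% per year instead of 3.0%
- Relative understatement: 2.55/23.29 = 11%. At a constant hazard this is the window divided by 18 months, so it does not depend on the rate: 10% for 55 days, 12% for 65.

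**If risk is higher just after stopping.** This is an assumption; the protocol gives no early hazard. With an early hazard twice the later 3% per year, early events are 5.10 and late events 20.74, so the rate is 5.10/25.84 = 20% low. At three times, it is 7.65/28.39 = 27% low.

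**When the bias is zero.** If early events are charged to untreated time, nothing is lost. If both events and time start at T3 and the hazard is constant, the rate is again 3%.

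**At the interim.** Assume uniform accrual of 1150 patients over 18 months and the blended rate 0.45 × 0.03 + 0.55 × 0.017 = 2.285% per year.
- At 1.5 years there are 1150 × 0.75 = 862.5 person-years and 862.5 × 0.02285 = 19.7 events, so the 20th event arrives at about 1.5 years.
- The untreated share is 0.0135/0.02285 = 59%, or about 12 of 20.
- Mean follow-up is about 0.75 year. The mean time spent in the 60-day (0.164-year) window is 0.164 × (1 − 0.164/3) = 0.155 year. The early share is therefore about 0.155/0.75, roughly one fifth, or about 2.4 events.
- The expected hazard ratio is 3/1.7 = 1.76. With one fifth of untreated events omitted it becomes about 1.76 × 0.8 = 1.4.

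This moves only one side. Off-drug, event-free time credited to apixaban lowers the apixaban rate and pushes the ratio up. Its amount depends on how many patients turn positive at T1 to T3, which the protocol does not give, so the net direction is open. Neither 1.76 nor 1.4 is near the stopping threshold of 3, so at the planning rates the decision itself would not change.

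**The case against.** The strongest reply is that the three groups are a follow-up list, not analysis sets. No sentence excludes a recurrence before T3, charges it to another group, or sets the time origin of a group rate. The follow-up sentence gives a duration, not a denominator. All primary events during follow-up are to be documented and adjudicated, and the schedule marks primary end-points for D-dimer-negative patients under T1, T2 and T3, so early events are collected. The interim rule names an untreated observation arm rather than group (a), and a patient who recurs off drug fits that description naturally. The other hazard ratios are planned for subgroup analyses, and the subgroups the protocol names are DVT and PE. Time origin and time-dependent exposure are often left to a statistical analysis plan.

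Most of this stands, and it rules out the stronger readings a reader might infer: that the untreated rate is understated, that early recurrences are dropped, or that the primary result is biased. The bias needs early events left out while their time is kept, and the protocol states no such combination. The primary end-point, the 3.5% limit and the sample size all concern the whole cohort, where a day-20 recurrence counts. The effect at constant hazard, 3.0% against 2.67%, also lies well inside the protocol's own 2.0 to 4.4% interval. A count of further off-drug events among patients who later turn positive would need figures the protocol does not give, so none is claimed.

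What does not fall is that the only written definition of the untreated group depends on a later result, and that a list presented as complete leaves some patients out. A stopping rule that compares arms also needs those arms fixed before the data are seen. A rate from T3 is legitimate for the decision taken at T3, but it does not describe the risk of the strategy from the day of stopping.

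**Conclusion.** The point holds in conditional form. Groups (a) to (c) have no place for a recurrence between stopping and T3, and they assign off-drug time by what happens later. Used as written for group rates or for the interim comparison, they can understate the untreated rate: about 2.6 of 23 expected events (1.7 to 3.7), 3.0% read as about 2.67% per year, 11% low. This rests on the protocol's 45% and 3% per year, a constant hazard from stopping, and a 60-day window. It would be 20 to 27% if the early hazard were two to three times the later one, and zero if early events are counted as untreated.

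At the interim about a fifth of untreated events would be at issue, under the accrual assumption above, and the net effect on the hazard ratio cannot be determined. The primary all-patient result is untouched. This is a modest ambiguity that should be closed because it bears on the low-risk-subset aim and on a stopping rule.

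**What to change.** For group rates, for any hazard ratio between treated and untreated patients, and for the interim rule, state that:

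- untreated time starts on the day anticoagulation stops after a negative T0;
- every primary event from that day until the first apixaban dose counts as untreated, whatever later tests show or would have shown;
- apixaban status is time-dependent, so a patient who turns positive at T1 to T3 contributes untreated time up to the first dose and apixaban time after it;
- the untreated arm of the interim rule is defined in these terms, including where patients who refuse apixaban belong;
- any rate that starts at T3 is a secondary, landmark estimate.

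The study must already hold the stopping and starting dates to time T1 to T3 and to dispense drug, so neither conduct nor sample size changes. The cost is slightly more analysis work and a slightly less favourable untreated rate than the groups as written could give.

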The latest ACCP international guidelines suggest an indefinite duration of anticoagulation in all patients after an unprovoked event, provided they are at low or moderate risk of bleeding ³. However, the rate of fatal bleeding while on indefinite treatment is comparable to that of fatal PE in patients in whom anticoagulation is discontinued ⁴, and the case-fatality rate of major bleeding is higher than that of symptomatic recurrent events ⁵. It should also be pointed-out that the ACCP guidelines propose a score to assess the individual bleeding risk which evaluates as at high bleeding risk subjects aged > 75 years. All these evaluations stem from studies in whom vitamin K antagonists (VKA) had been used for the secondary prevention of VTE disorders. Accordingly, most physicians do not accomplish these recommendations ⁶. In clinical practice, prolonging indefinitely anticoagulation beyond the first months appears a reasonable choice only in some categories of patients, including those with a personal or familiar history of VTE, those with known major thrombophilic disorders (such as deficiencies in the natural anticoagulants or the antiphospholipid syndrome), those with severe presentations (such as life-threatening PE) and those with a cava filter.

New scenarios have recently been offered by the use of the novel direct oral anticoagulants (DOACs), both for initial and standard anticoagulation course and for extended treatment. In particular for the last clinical scope, low-dose apixaban (2.5 mg BID) ⁷, aspirin (100 mg OD) ⁸, and sulodexide (500 mg BID) ⁹, proved effective (though with different extent) and with better safety results than expected by using VKAs. Indeed, randomized placebo-controlled clinical trials conducted in patients with unprovoked VTE who had received 3-12 months of conventional anticoagulation showed a reduction of the incidence of recurrent events of approximately 80% with low-dose apixaban ⁷, 35% with aspirin ⁸ and 50% with sulodexide ⁹, respectively.

Finally, in the DULCIS management study ¹⁰ it was shown that in patients with an unprovoked (or associated with a weak risk factor) symptomatic episode of proximal DVT and/or PE who had received a standard course of anticoagulation with VKA, serial D-dimer measurement in combination with the assessment of residual thrombosis in the deep leg veins is suitable in clinical practice to

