Based on a 2.2% annual event rate, a total sample size around 1150 patients and 18 months of follow-up, we expect around 38 recurrences and 2 major bleeding in our study. Since low-dose apixaban may be considered as the treatment gold-standard at the time of release of the study protocol, we plan an interim analysis when 20 primary endpoints are registered. The study will be interrupted if the relative risk of primary endpoints (HR) in the observational non-treatment arm will be >3 HR, with a p value <0.0001.

PROTOCOL SYNOPSIS

Title:	APIDULCIS: Extended anticoagulation with low-dose apixaban after a standard course anticoagulation in patients with a first venous thromboembolism who have positive D-dimer
Country:	Italy
Number of Sites:	53 centers
Research Hypothesis:	
The cumulative incidence of VTE recurrence 10 years after stopping anticoagulation is about 50% and 20% after a first unprovoked and provoked event respectively. It is not related to the duration of anticoagulant treatment. In addition, the rate of fatal bleeding on indefinite treatment is comparable to that of fatal PE in patients with anticoagulation discontinuation, and the case-fatality rate of major bleeding is higher than that of symptomatic recurrent events
 
The latest ACCP international guidelines suggest an indefinite duration of anticoagulation in all patients after an unprovoked event, at low or moderate risk of bleeding. All the available evaluations derive from studies on vitamin K antagonists (VKA) treatment. The use of the novel direct oral anticoagulants (DOACs) offers a valid alternative to vitamin k antagonist and in particular, for the extended treatment, low-dose apixaban (2.5 mg BID) proved effective with better safety results than VKA.
 
The DULCIS management study showed that in VKA patients with an unprovoked (or associated with a weak risk factor) symptomatic episode of proximal DVT, serial D-dimer measurement with the assessment of residual thrombosis allows to detect those VTE patients at low recurrence risk (annual rate, 3.0%) who can discontinue anticoagulation.
 
The latest ACCP guidelines suggest the use of D-dimer assessment after stop anticoagulation to decide the extended treatment.

Study Schema: Drugs / Doses / Length of Treatment)	Apixaban 2.5mg Treatment: 18 months

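### The planning rate gives the on-apixaban recurrence rate to every D-dimer-positive patient, yet untreated refusers are a planned group counted in the primary end-point, so the 80% power at 1148 and the 38 expected events assume essentially no refusal

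*Protocol*

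**What the plan says.** Statistical Considerations (Assumptions) splits the cohort into two parts that together make 100%. The 45% who stop anticoagulation carry an annual rate of about 3%. The rest are described as "In the remaining 55% of patients who will be encouraged to use apixaban", and for all of them "the expected rate of recurrent VTE is around 1.7% after the first year of treatment". The weighted sum is printed as 2.2%. The sample-size paragraph then gives 1148 patients for 80% power that the 95% confidence interval lies below 3.5%. The synopsis (Statistics) repeats the two-term rate, and its accrual goal is 1,200.

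Follow-up and Study End-points names three groups of included patients. Group (c) is "those with positive D-dimer who may refuse to assume apixaban as well as any other anticoagulant or antithrombotic agent for secondary VTE prevention". The primary efficacy end-point is "the composite of confirmed recurrent VTE and VTE-related death occurring during follow-up in all included patients". The assessment schedule gives refusers their own column, with the primary end-points marked and no study drug dispensed. D-dimer Assessment also provides for 18 months of follow-up when a D-dimer-positive patient declines to continue anticoagulation. The positives whom that section removes are those at T0 who choose to stay on a different anticoagulant.

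The interim-analysis section applies the 2.2% to about 1150 patients over 18 months: "we expect around 38 recurrences and 2 major bleeding in our study".

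**The concern.** The cohort being planned and the cohort being counted differ. The formula treats being offered apixaban as taking it, while the follow-up section foresees patients who take nothing and keeps them in the primary population. No refusal share, refuser rate or allowance in N is stated.

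The direction is not in doubt. The Background describes patients not identified as low risk as having a high risk of recurrence, and it credits low-dose apixaban with "a reduction of the incidence of recurrent events of approximately 80% with low-dose apixaban". Any plausible untreated rate in this group exceeds 1.7%, so leaving the group out overstates power and understates the event count. At stake is whether the 3.5% bound can be met even if the D-dimer rule performs exactly as assumed in everyone who follows it.

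**Working it through.** **Inputs from the Protocol.** Shares 45% and 55%; rates 3.0% and 1.7%; printed planning rate 2.2%; bound 3.5%; power 80%; N=1148; accrual goal 1,200; about 1150 patients over 18 months for the event count.

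**Assumptions (not in the documents).** f is the share of positives who refuse. r is their annual rate, taken at four values:
- 3%: a floor, equal to the D-dimer negatives;
- 5%: an intermediate value;
- 6.7%: 1 − 0.5^(1/10), from the Background's 50% at 10 years after unprovoked VTE, with a constant hazard;
- 8.5%: 1.7%/(1 − 0.80), from the Background's 80% reduction.

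**Step 1: reproduce 1148.** One-sample binomial formula with null and alternative variances and a one-sided 95% limit:

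n0 = [(1.645·√(0.035·0.965) + 0.842·√(0.022·0.978)) / 0.013]² = 1072.5

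Continuity correction: n0/4 · [1 + √(1 + 2/(n0·0.013))]² = 1148.2. This matches the stated figure.

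**Step 2: exact check.** With N=1148, the one-sided exact 95% upper limit is below 3.5% for at most 29 events. P(Bin(1148, 0.022) ≤ 29) = 80.6%. With N=1200 at most 31 events are allowed, and power at 2.2% is 84.3%.

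**Step 3: add refusers to the printed rate.** p = 0.022 + 0.55·f·(r − 0.017). For example, f = 10% and r = 8.5% give 0.022 + 0.55·0.10·0.068 = 2.574%, and P(Bin(1148, 0.02574) ≤ 29) = 51%. Ten percent of positives is 0.10·0.55·1148, about 63 patients.

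| r | f=5%, N=1148 | f=10%, N=1148 | f=5%, N=1200 | f=10%, N=1200 |
|---|---|---|---|---|
| 3% | 78% | 76% | 82% | 80% |
| 5% | 74% | 67% | 78% | 72% |
| 6.7% | 71% | 59% | 75% | 64% |
| 8.5% | 67% | 51% | 71% | 56% |

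At 1148, power falls below 80% once refusal exceeds 0.25% (r=8.5%), 0.5% (r=5%) or 1.3% (r=3%) of positives. At 1,200 the corresponding shares are about 1.8%, 3.7% and 9.5%.

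**Step 4: use the unrounded sum.** 0.45·0.03 + 0.55·0.017 = 0.0135 + 0.00935 = 2.285%, not 2.2%. A formula with a refuser term returns this value at f=0, so a restated table has to start there: p = 0.02285 + 0.55·f·(r − 0.017).

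| r | f=0, N=1148 | f=5%, N=1148 | f=10%, N=1148 | f=0, N=1200 | f=5%, N=1200 | f=10%, N=1200 |
|---|---|---|---|---|---|---|
| 3% | 74.7% | 72% | 69% | 78.8% | 76% | 74% |
| 5% | 74.7% | 68% | 60% | 78.8% | 72% | 65% |
| 6.7% | 74.7% | 64% | 52% | 78.8% | 68% | 57% |
| 8.5% | 74.7% | 60% | 44% | 78.8% | 64% | 48% |

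The drop from 80.6% to 74.7% at f=0 comes from the rounding and not from refusal. Only the further fall along each row is due to refusers.

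**Step 5: expected events over 18 months.** 1150·1.5·p. At 2.2% this is 37.95, the Protocol's 38. At 2.285% it is 39.4. At f=10% from 2.285%, p runs from 2.357% to 2.659%, giving 40.6 to 45.9 events.

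**The case against.** **The size rests on values the Protocol does not give.** This stands. The text says only that patients may refuse. Several features should keep group (c) small: patients who will not interrupt treatment for testing are excluded, positives at T0 who stay on another anticoagulant leave the study, participants are told beforehand what a positive result means, and the drug is supplied. Nothing supports a particular share such as 10%. The upper values of r are also borrowed. The 50% at 10 years is for unprovoked events, while the cohort also admits events with a removed risk factor, and the Background gives about 20% at 10 years after provoked events. The 3% row covers a much milder case, and at 1148 it still falls below 80%.

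**A reader might infer that the study has its stated power only if literally nobody refuses.** The documents do not support that. The 1,200 accrual goal absorbs a small refusal share on the printed 2.2%, although it is nowhere described as an allowance for refusal. Nor would zero refusal be enough, since the Protocol's own terms sum to 2.285%.

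**The loss depends on counting at 12 months.** The sizing uses an annual rate as a binomial proportion, but the end-point runs over at least 18 months. Suppose instead that an annual rate is estimated over 1148·1.5 = 1722 patient-years, with no losses and an exact one-sided Poisson limit. Then 47 events are allowed. From 2.2%, power is 94% with no refusal, 87-84% at f=5% and 78-69% at f=10% (r = 6.7-8.5%). The level is higher, but power still falls with refusal. The Protocol's 80% belongs to the 12-month calculation, so that is the figure to correct.

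**The synopsis says hypothesis testing is not needed.** True: it cites around 800 subjects and carries no 80% statement. The power correction therefore belongs in Statistical Considerations. The two-term rate and the 38 events appear in both places.

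**Conclusion.** The point holds. The planning rate applies the treated rate to all D-dimer positives, while the Protocol includes, follows and counts untreated refusers. The 80% at 1148 has almost no slack, so even about 1% refusal takes it below target at every r considered except the 3% floor, where the limit is 1.3%. At 5-10% refusal, power from the printed 2.2% is 78-67% and 76-51% over r = 3-8.5%.

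These figures rest on the assumed f and r, a one-sided exact 95% limit and a 12-month binomial count. They describe sensitivity to an undocumented assumption and do not forecast the trial's power. A reader might also conclude that N must rise or that refusers should leave the primary population. Neither follows: without a known f no new N can be derived, and counting refusers is consistent with evaluating a management procedure in all included patients.

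**What to change.** In Statistical Considerations and in the synopsis, write the planning rate as 0.45 × 3.0% + 0.55 × [(1 − f) × 1.7% + f × r], and state f and r with their source. Compute from the unrounded sum.

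In Statistical Considerations, replace the single 80% with power for both 1148 and 1,200 over a range of f. In the interim-analysis section and the synopsis, replace the 38 recurrences with the matching range: about 39 at f=0, and 41-46 at f=10% for r = 3-8.5%.

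Keep N, and keep refusers in the primary population. An estimate of the same composite in groups (a) and (b) may be added, labelled as descriptive support. It selects on acceptance after enrolment, and patients who discontinue early also contribute time off drug, so it cannot by itself attribute a missed bound to refusal.

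The cost is a few lines of text and one table. No additional patients are needed, but the stated power becomes less favourable.
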